10 INVESTIGATIONAL MEDICINAL PRODUCT / INVESTIGATIONAL DRUG

10.1 Investigational Medicinal Product (IMP)

The following medication supplies will be used in the study:

DS107 capsules:

Each DS107 capsule contains 500mg DGLA as an active ingredient in an opaque, oval soft gelatin capsule.

Placebo capsule:

Each matching placebo capsule contains 500mg of liquid paraffin in an opaque oval soft gelatin capsule.

10.2 Supply, Packaging, Labelling, Handling and Storage

DS107 capsules will be provided by the Sponsor as opaque, oval soft gelatin capsules containing 500mg of DGLA.

Placebo capsules will also be provided by the Sponsor as opaque, oval soft gelatin capsules containing 500mg of liquid paraffin.

DS107 capsules will be supplied in manufactured form (blinded), packaged in cold formed aluminium foil blisters of 28 units. Placebo will be presented in identical blisters and packs and stored/packaged the same as DS107 capsules. Study medication will be labelled according to US regulations.

The study medication will be provided by the Sponsor to the investigator and will be kept, on site, in a locked room or cabinet with limited access. DS107 and placebo capsules should be stored at a controlled room temperature between 15-25°C and will only be supplied to patients in the trial under the supervision of the investigator.

[figure not shown]
10.3 Dosage and Administration

This study involves a comparison of DS107 (2g and 1g) with placebo, administered orally once daily for a total duration of 8 weeks. **The last study drug administration should occur on the day preceding Week 8 (Visit 6) / Early Termination (ET) visit.** Patients will be randomized to one of the three treatment groups in a 1:1:1 ratio:

- Treatment group A: 1g DS107 (2 DS107 capsules and 2 placebo capsules) administered once-daily for 8 weeks
- Treatment group B: 2g DS107 (4 DS107 capsules) administered once-daily for 8 weeks
- Treatment group C: Placebo (4 placebo capsules) orally administered once-daily for 8 weeks

Patients will be required to administer the drug 2 hours after the consumption of food. Medication(s) for other conditions that are permitted in the study can be taken as usual.

Blister packs will consist of 7 rows of 4 capsules with each weekday detailed. Each row constitutes one dose. Patients will be instructed to take the 4 capsules **from left to right**, on the relevant day, as shown below:

To maintain the blind throughout the study, the DS107 capsules and placebo capsules will be identical in appearance.

10.4 Duration of Treatment

Patients will be orally administered DS107 or placebo once daily for 8 consecutive weeks.

10.5 Methods for Assigning Patients to Treatments

Approximately 300 patients will be randomized into double-blind treatment groups in a 1:1:1 ratio by an Interactive Web Response System (IWRS) as follows:

- Treatment group A: 1g DS107 (2 DS107 capsules and 2 placebo capsules) administered once-daily for 8 weeks
- Treatment group B: 2g DS107 (4 DS107 capsules) administered once-daily for 8 weeks
- Treatment group C: Placebo (4 placebo capsules) orally administered once-daily for 8 weeks

A randomization list permuted blocks and stratified by site will be generated by the Sponsor or its designee. The randomization schedule with study drug assignments will be generated prior to the start of the study and will be known only to the individuals responsible for labelling the study drug, the statisticians generating the schedule and the IWRS team responsible for implementing the schedule. The IWRS will assign a medication kit number to each patient and the contents will be based on the randomization code.

At the investigational site, each patient will be assigned a patient identifier number during screening that will be used on all patient documentation. The patient identifier number will

contain the site number and the patient number assigned in numerical order at the screening visit (e.g.: 102-10 for the tenth patient screened at the site number 02). Patient numbers will be assigned in ascending order starting with 01.

10.6 Drug Accountability

All IMPs supplies for this study must be retained in a safe place at all times of the study. Only personnel authorised by the principal investigator at each site should dispense the IMP and the accountability is the responsibility of the Investigator. The Investigator or pharmacist must complete the IMP supply form, verifying the receipt of IMP. The patients should return all used and unused packs of IMP to the study site at every visit. Following compliance assessment the packs of IMP will be retained in a secure location at the site until the end of the study. After the Clinical Research Associate (CRA) has completed a final drug accountability review the IMP may be returned or destroyed only when instructed by the CRA.

11 ADVERSE EVENTS AND SERIOUS ADVERSE EVENTS

11.1 Definitions of Adverse Events

11.1.1 Seriousness

Adverse Events (AE):

Any undesirable experience occurring to a patient that has signed the ICF and who has taken their first dose of the study drug, whether or not considered related to the investigational IMP(s). All AEs must be recorded in the case report form, defining relationship to IMP and severity. AEs should also be recorded by the Investigator in the patient file/notes.

Serious Adverse Events (SAE):

If a patient experiences a serious adverse event after the first dose of the study drug, the event will be recorded as a serious adverse event.

A serious adverse event (experience) or reaction is any untoward medical occurrence that at any dose:

- results in death
- is life-threatening
- requires in-patient hospitalization or prolongation of existing hospitalization
- results in persistent or significant disability/incapacity, or
- is a congenital anomaly/birth defect

Note: The term "life-threatening" in the definition of "serious" refers to an event in which the patient was at risk of death at the time of the event. It does not refer to an event which hypothetically might have caused death if it were more severe.

Medical and scientific judgment should be exercised in deciding whether expedited reporting is appropriate in other situations, such as important medical events that may not be immediately life-threatening or result in death or hospitalization but may jeopardize the patient or may require intervention to prevent one of the other outcomes listed in the definition above. These should also usually be considered serious.

Examples of such events are intensive treatment in an emergency room or at home for allergic bronchospasm, blood dyscrasias or convulsions that do not result in hospitalization, or development of drug dependency or drug abuse.

Unexpected Adverse Event (UAE):

An experience not previously reported in the Investigator's Brochure or similar product information sheet such as the Summary of Products Characteristics (SPC).

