8 STUDY CONDUCT

8.1 Study Schedule

During the study, six visits to the clinic are scheduled at least one week after the screening visit: one at the start of the comparative treatment period/baseline (Day 0/Visit 2) and five in the comparative treatment period (Week 2/Visit 3, Week 4/Visit 4, Week 6/Visit 5 and Week 8/Visit 6). A final safety follow-up visit (Visit 7) will be conducted two weeks after Visit 6 or two weeks after the final visit attended if the patient does not complete the study. The baseline visit must be performed, at the latest 30 days after the screening visit.

Patients who discontinue the study early will be asked to attend the investigative site as soon as possible so that assessments scheduled for Visit 6 can be conducted at an Early Termination visit.

In the event that treatment is occurring, a wash out period of up to 4 weeks may be necessary. At the Screening visit, after giving informed consent to participate, patients will be assessed using the screening examinations. Eligible patients with confirmed AD using the Hanifin and Rajka criteria and who meet all the inclusion criteria and do not meet the exclusion criteria at the baseline visit will be enrolled.

During the treatment period and follow-up period patients will be restricted from using any other treatment for AD, with the exception of the same emollients they have been consistently using at the baseline visit. Any medication (prescription as well as OTC drugs) or therapeutic intervention deemed necessary for the patient, and which in the opinion of the Investigator do not interfere with the safety and efficacy evaluations, may be continued. A list of ‘medications and therapeutic regimens excluded from the study’ is defined below (Section 9.2.11.2).

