9.2 Safety Assessments

9.2.1 Medical / Surgical History

A complete review of the patient’s medical history will be undertaken by the Investigator or designee at the Screening visit (Visit 1) to ensure that no exclusion criteria have been met. Any concomitant disease, whether considered relevant for the study or not by the Investigator, must be reported in the CRF. The date of diagnosis or duration of the condition should be noted where possible..

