9.2.3 Vital Signs

Vital signs measurements will be performed as per the Study Flow Chart (Appendix 1) at every visit. Measurements to be taken include:

- Blood pressure: will be performed as supine (after at least 5 minutes of rest) systolic and diastolic blood pressure (in mmHg)
- Heart rate: taken at rest (in bpm)
- Temperature: will be taken as per clinic practice. Temperature and route will be recorded in the CRF.

Vital signs measurements will be performed before any blood samples are taken. All new findings or changes to previous findings considered clinically significant will be recorded in the CRF as an AE if the finding is made after the patient has signed the ICF.

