15 APPENDICES

15.1 Appendix 1: Study Flow-Chart

Visit	Screening/ Visit 1	Baseline / Visit 2	Week 2 / Visit 3	Week 4 / Visit 4	Week 6 / Visit 5	Week 8 / Visit 6 / Early Termination	Week 10 / Visit 7 / Follow up
Day	-30 to -1	0	14	28	42	56	70
Visit Window			+/-2 days	+/-2 days	+/-2 days	+/-2 days	+/-3 days
Informed Consent	X						
Assign Patient identifier number	X						
Demographics	X						
Medical / Surgical History	X						
Review Inclusion/Exclusion Criteria	X	X					
Hanifin and Rajka criteria	X	X					
Randomization		X					
Safety labs: Serum Biochemistry (including FSH levels at screening when applicable ¹), Hematology, Urinalysis	X	X				X	X ²
Pharmacokinetic Sampling		X		X		X	X
Biomarker Sampling		X				X	
Pregnancy Test (β-hCG if female of childbearing potential)	X					X	
Vital Signs	X	X	X	X	X	X	X
Physical Examination ³	X	X	X	X	X	X	X
BMI	X	X				X	
Dispense Study Drug ⁴		X	X	X	X		
Collect Study Drug			X	X	X	X	
Dispense Patient Compliance Log		X	X	X	X		
Collect and Review Patient Compliance Log			X	X	X	X	
IMP Accountability			X	X	X	X	
BSA	X	X	X	X	X	X	X
IGA	X	X	X	X	X	X	X
EASI assessment	X	X	X	X	X	X	X
NRS Pruritus assessment ⁵	X	X-----X					
DLQI questionnaire		X	X	X	X	X	X
POEM questionnaire		X	X	X	X	X	X
PGI-S questionnaire		X	X	X	X	X	X
PGI-C questionnaire		X	X	X	X	X	X
Concomitant Medications	X	X	X	X	X	X	X
Emollient use capture ⁵		X-----X					
Adverse Events ⁶		X	X	X	X	X	X

1. FSH requirement to confirm female non-child-bearing potential for women greater than 40 years of age who have had a cessation of menses for at least 12 months. Non-child bearing potential may also be confirmed via cessation of menses for at least 24 months without FSH levels confirmed.
2. Only if a laboratory AE recorded at Week 8. In that case only the sample which is the cause of the AE should be re-tested.
3. Physical Examination will be symptom-directed as per section 9.2.2.
4. Patients will be instructed to take their last study drug dose the day preceding Week 8 visit.
5. NRS/Emollient use will be captured electronically through the IWRS by the patient. Patients may use paper to document these assessments also.

6. Collection of AE will start after the first study drug administration.

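### AE and SAE recording starts at the first dose, so a serious event in the post-consent washout triggers no report, and the vital-signs section contradicts that start point

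*Protocol*

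**What the plan says.** **Start of participation.** Protocol section 7 counts a patient as included from signature of the consent form. Section 8.1 then states: "In the event that treatment is occurring, a wash out period of up to 4 weeks may be necessary". It also sets an outer limit: "The baseline visit must be performed, at the latest 30 days after the screening visit". Exclusion criteria 2 and 3 (section 7.3) set the periods: 4 weeks off systemic AD treatment and 2 weeks off topical medicated treatment before baseline.

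**Start of AE and SAE recording.** Section 11.1.1 defines an AE as "Any undesirable experience occurring to a patient that has signed the ICF and who has taken their first dose of the study drug". Its SAE rule opens: "If a patient experiences a serious adverse event after the first dose of the study drug". Appendix 1, footnote 6, says: "Collection of AE will start after the first study drug administration". The baseline visit text in section 8.2.3 agrees.

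**The conflicting rule.** Section 9.2.3 says that clinically significant new or changed vital-sign findings "will be recorded in the CRF as an AE if the finding is made after the patient has signed the ICF".

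**Medical history.** Section 9.2.1 places the review "at the Screening visit (Visit 1) to ensure that no exclusion criteria have been met". Appendix 1 schedules it at that visit only.

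**Analysis.** Section 11.1.4 requires AE start and end dates in the CRF. SAP 2.2.13.3 presents only treatment-emergent events, defined by an onset date on or after the date of first dose.

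**The concern.** The study itself may require a consented patient to stop AD treatment. The foreseeable harm of doing so is a flare, and it would fall between consent and first dose. In that interval the protocol has no AE, no SAE and no duty to report within 24 hours. What is at stake is first the sponsor's sight of serious harm caused by a study procedure.

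The second issue is consistency. Vital signs are measured at screening and at baseline, both before dosing. The same abnormal reading is an AE under section 9.2.3 and not one under section 11.1.1, so what reaches the database depends on which section a site follows.

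The third issue is smaller. A condition that begins in the gap has no designated place in medical history or among the AEs. If it is first written down after dosing, its onset has to be reconstructed.

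**Working it through.** The plan states no figure on this point, so there is nothing to reproduce. The check compares the rules and then sizes the gap.

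**1. Which rule applies before the first dose?**

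| Source | Start point |
|---|---|
| Protocol 8.2.3, AE collection | after first dose |
| Protocol 11.1.1, AE definition | consent signed and first dose taken |
| Protocol 11.1.1, SAE recording | after first dose |
| Protocol Appendix 1, footnote 6 | after first dose |
| Protocol 9.2.3, vital signs | ICF signature |
| SAP 2.2.13.4, clinically significant labs | AE, no start point given |

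The 24-hour report in section 11.1.4 applies to potential SAEs and so inherits the section 11.1.1 rule. No section of either document provides for SAE reporting between consent and first dose.

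**2. Does the washout fall inside the unrecorded interval?** The maximum washout is 28 days and the maximum time from screening to baseline is 30 days. Since 28 < 30, a full washout fits between the consent visit and the first dose.

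**3. Size of the gap.** Section 8.1 gives 7 days as the minimum and 30 as the maximum. Follow-up from first dose to Week 10 is 70 days (Appendix 1). The unrecorded share is gap / (gap + 70).

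- 7 days: 7/77 = 9.1%
- 14 days (topical washout): 14/84 = 16.7%
- 28 days (systemic washout): 28/98 = 28.6%
- 30 days: 30/100 = 30.0%

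For 300 randomised patients:

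- 7-day gap for all: 300 × 7 / 365 = 5.8 patient-years
- 30-day gap for all: 300 × 30 / 365 = 24.7 patient-years
- post-dose follow-up: 300 × 70 / 365 = 57.5 patient-years

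The screening window in Appendix 1 reads Day -30 to -1. A 1-day gap would give 1/71 = 1.4%, but section 8.1 asks for at least a week. Screen failures are not counted.

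**4. Can a pre-dose event enter the treatment-emergent tables?** A correctly dated event from before the first-dose date cannot, because its onset fails the SAP rule. Two routes remain.

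- *Misdated onset.* A condition that arose in the gap is first recorded at a later visit with a wrong start date. Taking medical history only at screening makes this more likely, as does a baseline examination that is symptom-directed (section 9.2.2).
- *Day 0.* SAP 2.2.5 puts the first dose at the site on Day 0, after the baseline assessments. A site that follows section 9.2.3 and records a pre-dose vital-sign finding with Day 0 onset satisfies onset date ≥ first-dose date. The finding is then counted as treatment-emergent with no dating error at all. A site that follows section 11.1.1 records nothing. This route needs the first dose to be taken on Day 0.

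**The case against.** The strongest reply is that three places in the protocol agree on the first dose, that only one sentence about vital signs differs, and that recording from first dose is a legitimate choice when the analysis concerns treatment-emergent events. The patient is also not unobserved. Visit 2 repeats vital signs, examination, safety laboratory tests, disease scores and concomitant medication. Medications are recorded with indication and start date from 30 days before screening. Section 8.2.1 allows unscheduled visits for an AE or a marked change in disease. Eligibility is verified again at Visit 2, and active skin infection is an exclusion.

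Much of this stands, and it rules out three stronger readings.

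- A reader might infer that washout events will routinely be counted as on-treatment events. The required start dates and the SAP onset-date rule prevent that for correctly dated events from before the first-dose date. Assignment is randomised and double-blind, so any misdating should fall about equally on the arms and add noise rather than bias the comparison.
- A reader might infer that nothing is on record about a patient's condition at first dose. The Visit 2 assessments show otherwise.
- A reader might set 24.7 patient-years against the 46.0 of treatment (300 × 56 / 365) and take it as unobserved washout. That figure needs every patient to use all 30 days. It is screening time, and washout is conditional. The percentages rest on 70 days of follow-up, so the matching comparator is 57.5.

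The reply does not reach the main point. Repeating assessments at Visit 2 does not make a hospitalisation in the third week of washout reportable, and it gives nothing on a patient who never reaches Visit 2. An investigator may choose to report such an event, but the protocol does not ask for it.

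**Conclusion.** The point holds in two parts. First, a serious event during a study-required washout is outside the SAE rule and does not trigger the 24-hour report. Second, section 9.2.3 contradicts sections 8.2.3 and 11.1.1 and Appendix 1 on when a finding becomes an AE.

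The gap is 7 to 30 days per patient, or 9% to 30% of post-consent time to Week 10. For 300 patients the range is 5.8 to 24.7 patient-years, depending on whether all use the shortest or the longest interval. This rests on the section 8.1 limits, a 365-day year and full follow-up to Day 70. It measures time, not harm: the documents give no event rate for the screening period and do not say how many patients will need a washout.

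Miscounting as treatment-emergent is a limited residual risk, confined to misdated onsets and to pre-dose findings on Day 0. The between-arm safety comparison is not seriously threatened. The case for change is patient safety and consistent recording at low cost.

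**What to change.** - Reconcile Protocol 8.2.3, 9.2.3, 11.1.1 and Appendix 1 (footnote 6) to one start point: record AEs and SAEs from ICF signature, with the same 24-hour SAE report, and flag each as pre-dose or post-dose.
- Add an update of ongoing conditions at Visit 2, before dosing, so that anything that began after screening is on record with its onset.
- In SAP 2.2.13.3, keep the onset-date rule and add the flag to the derivation, so that a pre-dose Day 0 event is not counted as treatment-emergent.

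The cost is amendment wording, one eCRF field and a small change to the derivation. The downside is some extra data entry for the screening period, including for screen failures, on whom section 12.10 already collects limited data. The treatment-emergent tables change only by dropping pre-dose Day 0 events.

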11.1.2 Severity

The intensity of an AE is an estimate of the relative severity of the event made by the investigator based on his or her clinical experience. The following definitions are to be used to rate the severity of an AE:

- Mild: The adverse event is transient and easily tolerated.
- Moderate: The adverse event causes the patient discomfort and interrupts the patient's usual activities.

- **Severe:** The adverse event causes considerable interference with the patient's usual activities, and may be incapacitating or life-threatening.

11.1.3 Relationship to IMP

The investigator will establish causality of the AE to experimental treatment. The investigator should take into account the patient's history, most recent physical examination findings, and concomitant medications.

The following definitions will be used to determine causality of an AE:

- **Not related:** temporal relationship of the onset of the AE, relative to the experimental treatment is not reasonable or another cause can explain the occurrence of the AE.
- **Related:** temporal relationship of the onset of the AE, relative to the experimental treatment is reasonable, follows a known response pattern to the treatment, and an alternative cause is unlikely.

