11.2 Serious Adverse Reactions and Unexpected Adverse Reactions

11.2.1 Definitions

Adverse Reaction:

All noxious and unintended responses to a medicinal product related to any dose should be considered adverse drug reactions.

The phrase "responses to a medicinal product" means that a causal relationship between a medicinal product and an adverse event is at least a reasonable possibility i.e. the relationship cannot be ruled out.

For marketed medicinal products, an adverse reaction is a response to a drug which is noxious and unintended and which occurs at doses normally used in man for prophylaxis, diagnosis, or therapy of disease or for modification of physiological function.

Unexpected Adverse Reaction:

An adverse reaction, the nature or severity of which is not consistent with the applicable product information (e.g. Investigator's Brochure for an unauthorised investigational product or similar product information sheet such as the Summary of Products Characteristics (SPC)).

Suspected Unexpected Serious Adverse Reaction (SUSAR):

Any serious adverse reaction that might be related to the IMP and are unexpected according to the definition above.

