12.9.4 Safety variables

The type and frequency of adverse events will be summarised by MedDRA system organ class and preferred term per treatment group. In addition, the number and proportion of patients with at least one adverse event will be summarised per treatment group.

The number and proportion of patients experiencing serious adverse events, adverse events leading to withdrawal and adverse events possibly or probably related to treatment will be summarized per treatment group. The secondary safety analysis will be based on the Safety Analysis Set only.

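### The causality scale in Protocol 11.1.3 is narrower than the protocol's own definition of an adverse reaction, leaves one kind of event unclassified, and does not match the summary planned in 12.9.4

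*Protocol*

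**What the plan says.** Protocol 11.1.3 is binding on the investigator: "The following definitions will be used to determine causality of an AE". It offers two levels.

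- *Related*: the timing is reasonable, and the event "follows a known response pattern to the treatment, and an alternative cause is unlikely". The conditions are joined by 'and', so all three must hold.
- *Not related*: the timing "is not reasonable or another cause can explain the occurrence of the AE". Either condition is enough.

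Protocol 11.2.1 defines an adverse reaction differently, as a response whose causal relationship to the product "is at least a reasonable possibility i.e. the relationship cannot be ruled out". An unexpected adverse reaction is "An adverse reaction, the nature or severity of which is not consistent with the applicable product information". A SUSAR is "Any serious adverse reaction that might be related to the IMP and are unexpected according to the definition above".

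Protocol 11.1.4 requires a relationship to be recorded for every AE. It also requires every potential SAE to be notified to the pharmacovigilance CRO within 24 hours, with the investigator's preliminary view of causality.

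For the analysis, Protocol 12.9.4 states that "adverse events possibly or probably related to treatment will be summarized per treatment group". SAP 2.2.13.3 instead uses a related/not-related split: it tabulates subjects with any IMP-related AE and with IMP-related SAEs, by treatment group and for the two DS107 doses combined.

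**The concern.** Three parts of one protocol describe causality in three ways, and nothing says which prevails. The investigator works from 11.1.3, the strictest. The definition of an adverse reaction in 11.2.1 is wider. The summary in 12.9.4 needs categories that 11.1.3 never collects.

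The known-pattern condition is the main difficulty. A reaction of a kind not seen before has no known pattern, so it cannot satisfy *Related* however suggestive its timing. The other difficulty is that *Not related* applies as soon as another cause can explain the event, even if the drug remains a reasonable candidate.

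At stake are the IMP-related rows of the safety tables, which rest directly on the investigator's label, and, less directly, the recognition of SUSARs.

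**Working it through.** The documents give no figure to reproduce here, so the check is logical. Take three yes/no conditions from 11.1.3:

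- T: the timing is reasonable.
- K: the event follows a known response pattern.
- A: another cause can explain the event. The alternative being unlikely, as *Related* requires, is read as 'not A'.

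Then *Related* = T and K and not A, and *Not related* = not T, or A. Three conditions give 2 × 2 × 2 = 8 combinations.

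| Timing reasonable (T) | Known pattern (K) | Other cause (A) | Level under 11.1.3 | Can it meet the 11.2.1 threshold? |
|---|---|---|---|---|
| yes | yes | no | Related | yes |
| yes | no | no | neither | yes |
| yes | yes | yes | Not related | yes, if the drug cannot be excluded |
| yes | no | yes | Not related | yes, if the drug cannot be excluded |
| no | any (2) | any (2) | Not related (4 combinations) | not considered further |

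Totals: Related 1; Not related 2 + 4 = 6; neither 1; sum 8.

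Among the 4 combinations with reasonable timing, 1 is *Related*. The other 4 − 1 = 3 can still satisfy 11.2.1. These are counts of logical cases, not of patients or events, and they say nothing about how often each case arises.

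The unclassified row also fits the separate definition of an unexpected adverse event in Protocol 11.1.1, when the event is new in kind: "An experience not previously reported in the Investigator's Brochure or similar product information sheet". Since 11.1.4 obliges the investigator to record a relationship, a level must be chosen for such an event, and the text supports neither.

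Reading the two wordings about other causes as exact opposites favours the protocol. If an alternative is possible but improbable, an event with good timing and a known pattern could meet both definitions at once.

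Setting 11.1.3 beside 12.9.4: a record made on the two-level scale cannot be divided into possible and probable relationships, so the 12.9.4 summary cannot be produced as worded. The SAP's related/not-related rows can be produced, but they inherit the narrow rule.

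**The case against.** The strongest reply is that the practical damage is limited, and much of it stands.

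**Unexpected reactions are not all barred.** A reader might infer that no unexpected reaction can ever be *Related*. The documents do not support that. Section 11.2.1 counts a reaction as unexpected on nature or on severity, and one that is unexpected only in severity may follow a known pattern. Nor does the protocol equate a known response pattern, which it leaves undefined, with listing in the Investigator's Brochure. The bar applies to reactions new in nature.

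**SUSAR reporting has another route.** A reader might infer that SUSARs will be missed. Every potential SAE goes to the pharmacovigilance CRO whatever its causality, the investigator's view is only preliminary, and 11.2.1 frames a SUSAR by whether it might be related. The CRO could apply that wider test. However, neither 11.1.4 nor 11.2.2 describes reassessment of the investigator's call, so the risk remains.

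**The direction of the unclassified case is unknown.** Such an event is not *Not related* either, and an investigator might call it *Related* out of caution. That is fair, but doing so departs from the text. It does not help the two well-timed cases with another possible cause, which the text sends to *Not related*.

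**No arm is singled out.** A reader might infer that the rule flatters DS107 in particular. Sites are blinded and one definition covers all arms, so no arm-specific effect is shown.

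**Events are not lost.** SAP 2.2.13.3 also tabulates all treatment-emergent AEs, SAEs and deaths regardless of causality, and tests system organ classes at 2% or more. The effect is confined to the rows that use causality.

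**Prior exposure does not size the problem.** The 87 people given the capsules so far limit what could have been seen. A bound on the incidence of an unseen reaction is not a rate of under-calling.

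**Conclusion.** The concern holds as an inconsistency among Protocol 11.1.3, 11.2.1 and 12.9.4. It has a definite direction. Applied as written, 11.1.3 labels fewer events *Related* than the protocol's own adverse-reaction definition would, so the IMP-related AE and SAE rows in SAP 2.2.13.3 are under-counted by that standard. One of the eight logical cases has no level at all, and the 12.9.4 categories do not exist on the scale.

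The number of events affected cannot be derived from the documents. The conclusion assumes that investigators follow 11.1.3 literally and that 11.2.1 states the intended meaning of a reaction. For SUSARs, the finding is a risk that a case is missed and no more than that. The point deserves correction because the wording is operational and the remedy is simple; it does not undermine the comparison of overall AE rates.

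**What to change.** Reconcile the three sections to one causality definition and one set of levels.

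1. In Protocol 11.1.3, define *Related* by the criterion already in 11.2.1 (a causal relationship is at least a reasonable possibility) and remove the known-pattern condition.
2. Define *Not related* as the complement, so that every event falls in exactly one level. The presence of another possible cause would then be weighed in the judgement and would not settle it alone.
3. In Protocol 12.9.4, replace the possible and probable categories with *related*. The SAP already works with two levels, so its categories need no change.

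The cost is protocol wording and guidance to sites. Design, sample size and treatment are untouched. The related-AE count may rise somewhat in all arms, placebo included.
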